8 TRIAL DESIGN

8.1 Overall trial design and schedule of events

The trial is a Phase I trial divided into 2 parts. Part A is double-blind, placebo-controlled, and designed to evaluate the safety, tolerability, and PK after topical administration of single ascending doses of GZ21T in healthy male and female volunteers. Part B is open-label and designed to evaluate the optimum amount of cream applied to a given body area (dose/area) of single doses of GZ21T in healthy volunteers.

In Part A, participants will receive a single topical application of GZ21T or placebo in 2 sequential cohorts (cohorts 1 and 2) followed by 2 cohorts starting in parallel (cohorts 3 and 4) with planned doses as follows:

In Part B, participants in cohort 1 will receive a single topical application of GZ21T. Based on the extent of the cream's absorption, up to 2 additional cohorts can be explored (optional cohorts 2 and 3). The maximum administered dose will not exceed 25.5 mg/cm².

The trial design and the proposed dose levels are shown in Figure 8.1-1. The rationale for the proposed starting dose and the planned dose escalation is detailed in Section 8.3.

In Part A, participants will come for 3 visits to the research clinic for screening, treatment, and follow-up. Screening (Visit 1) will take place between Day -28 and Day -1. Eligible participants will be admitted to the research clinic between Day 1 and Day 2 (Visit 2) for randomisation, IMP administration and pre- and post-dose safety and PK assessments.

In each cohort, a single dose of the IMP will be topically applied to the selected area. The treated area will be marked with a medical skin waterproof marker. During that time, participants should remain still without touching the treated area. Before treatment on Day 1, participants must have abstained from using moisturising ointments, creams, or emollients for 24 hours on the area to be treated.

Sentinel dosing will be applied. The first 2 participants in each cohort will receive either GZ21T or a placebo as randomised. After the sentinel participants, at least 24 hours must pass before dosing of the remaining participants to give sufficient time for the observation of any reactions.

All participants will be carefully monitored by clinical staff during and after IMP application and will remain at the research clinic for at least 24 hours after treatment (Day 2) for safety assessments, including safety laboratory testing, 12-lead electrocardiogram (ECG), vital signs, local tolerability and AEs, and PK assessments. Participants will return to the research clinic on Day 7±1 day (Visit 3) for final safety and PK assessments.

Before initiating a new cohort, all participants in the previous cohort(s) must have been dosed and observed for at least 24 hours for safety and tolerability and to obtain blood samples for PK analysis. The PK data, up to and including 24 hours data, for all treated participants must have been reviewed by the iSRC before initiating a new cohort. Once safety, tolerability, and PK data of the last participant in each cohort has been collected, there must be at least 1 week between dose escalations to allow for a thorough evaluation of data.

Each participant is expected to participate in Part A of the trial for a maximum of 35 days including an up to 28-day screening period.

The overall schedule of events for Part A of the trial is shown in Table 8.1-1, and the detailed schedule of events for Visit 2 is shown in Table 8.1-2. Trial assessments are described in Section 11.

In Part B, Participants will come for 3 visits to the research clinic for screening, treatment, and follow-up, and will have 1 remote telephone visit. Screening (Visit 1) will take place between Day -28 and Day -1. Eligible participants will visit the research clinic on Day 1 (Visit 2) for IMP administration cream absorption evaluation and local tolerability assessments.

A single dose of the IMP will be topically applied to the selected area. The treated area will be marked with a medical skin waterproof marker. During that time, participants should remain still without touching the treated area. Before treatment on Day 1, participants must have abstained from using moisturising ointments, creams, or emollients for 24 hours on the area to be treated.

All participants will be carefully monitored by clinical staff during and after IMP application and will remain at the research clinic for 2 hours after treatment for local tolerability and AE evaluation. On Day 2 (Visit 3), approximately 24 hours post-dose, participants will visit the research clinic for follow-up of local tolerability and AEs. A remote telephone call will be performed on Day 7 ±1 day (Visit 4) to follow-up on local tolerability and AEs.

Each participant is expected to participate in Part B of the trial for a maximum of 35 days, including an up to 28-day screening period.

The schedule of events for Part B of the trial is shown in Table 8.1-3 and the detailed schedule for Visit 2 and Visit 3 is shown in Table 8.1-4. Trial assessments are described in Section 11.

Table 8.1-1 Overall schedule of events (Part A)

Assessment↓/Day→	CTP section	Screening	Inpatient stay		Follow-up/End-of-trial
		Visit 1	Visit 2 ¹		Visit 3 ²
Informed consent	11.2.1	X			
Eligibility criteria	9.4/9.5	X	X ³		
Demographics	11.2.3	X			
Weight/height/BMI/BSA ⁴	11.2.4	X			
Medical/surgical history	11.2.5	X			
HIV, hepatitis B and C	11.2.6	X			
Physical examination	11.3.6	X	X	X ⁵	X ⁵
Pregnancy test ⁶	11.2.7	X	X		
Urine drug screen	11.2.8	X	X		
Alcohol test	11.2.9	X	X		
Safety laboratory profile ⁷	11.3.5	X	X	X	X
12-lead ECG	11.3.4	X	X	X	X
Vital signs ⁸	11.3.3	X	X	X	X
Local tolerability ⁹	11.3.2		X	X	X
Randomisation	9.9		X		
IMP administration	10.5		X		
PK blood sampling	11.4.1		X	X	X
Meals ¹⁰	-		-----X-----		
Baseline symptoms ¹¹	11.2.10	X			
Adverse events ¹²	11.3.1		-----X-----		
Prior and concomitant medications	11.2.11	-----	-----X-----		

BMI=body mass index, BSA=body surface area, ECG=electrocardiogram, HIV=human immunodeficiency virus, IMP=investigational medicinal product, PK=pharmacokinetic,

1. Detailed schedule for Visit 2 is shown in Table 8.1-2.

2. Or after early withdrawal.

3. Confirmation of eligibility criteria, prior to IMP administration.

4. BSA will be calculated from the weight and height.
5. Symptom-driven physical examination.
6. Women of childbearing potential (WOCBP) only. At screening: plasma/serum test. At other visits: urine test.
7. Clinical chemistry, haematology, and coagulation.
8. Blood pressure, and pulse.
9. Dryness and discoloration will be assessed pre-dose, and 24 hours and 7 days post-dose.

3. Confirmation of eligibility criteria, prior to IMP administration.
4. BSA will be calculated from the weight and height.
5. WOCBP only. At screening: plasma/serum test. At other visits: urine test.

6. Clinical chemistry, haematology, and coagulation.
7. Blood pressure, and pulse.
8. Local tolerability assessments will be done 2 hours post-dose. Dryness and discolouration will be assessed pre-dose, and 24 hours post-dose.
9. Baseline symptoms will be recorded up until the administration of IMP on Day 1.
10. AEs will be recorded from the first administration of IMP.

Table 8.1-4 Detailed schedule of events for Visit 2 and Visit 3, Part B

Day→	Day 1						Day 2
Assessment↓/Time→	Pre-dose	0	15 min	30 min	1 h	2 h	24 h
Eligibility criteria	X						
Urine drug-screen	X						
Alcohol test	X						
Pregnancy test (WOCBP)	X						
Local tolerability	X					X ⁰	X ²
IMP administration		X					
Cream absorption evaluation (photography)			X	X	X	X	
Cream absorption evaluation (visual inspection by trial staff)				X	X	X ⁰	
Baseline symptoms	X						
Adverse events					X		
Prior and concomitant medications				X			

WPBCP=women of childbearing potential

1. Participants will be discharged from the research clinic after the local tolerability and cream absorption assessments at 2 hours.
2. Dryness and discoloration will be assessed pre-dose and 24 hours post-dose.

8.2 Rationale for trial design

The European Medicines Agency (EMA) guideline EMEA/CHMP/SWP/28367/07 Rev. 1 on strategies to identify and mitigate risks for FIH and early clinical trials [3] has been considered when designing this trial.

In Part A, the design of the trial is based on the aim to study the safety, tolerability, and PK of selected doses of GZ21T in a limited number of healthy male and female volunteers. The trial involves careful monitoring of the participant's well-being and will provide important safety and PK data to support the design of further trials, both in healthy volunteers and in patients. The length of the trial and time points for PK blood sampling were selected based on data obtained from previous non-clinical and clinical trials.

A placebo control will be used to establish the frequency and magnitude of changes in primary and secondary endpoints that may occur in the absence of active treatment, in compliance with the relevant International Council for Harmonisation of Technical Requirements for Pharmaceuticals for Human Use (ICH) guidelines [4-6].

Randomisation will be used to minimise bias in the assignment of participants to treatment groups and to increase the likelihood that known and unknown participant attributes (e.g., demographic and baseline characteristics) are evenly balanced.

Blinded treatment will be used to reduce potential bias during data collection and the evaluation of endpoints.

In Part B, the design of the trial is based on the aim to study the optimal amount of cream suitable for daily use to be applied in a limited number of healthy male and female volunteers. In order to achieve the objectives of this part of the trial, a placebo group is not required.

8.3 Selection of starting dose and rationale for planned dose escalation

8.3.1 Selection of starting dose

The drug compound G17-6.02 has previously been given orally to approximately 40 patients with solid tumours and lymphoma, at dose levels up to [REDACTED] mg two times daily (BID). In that study, 375 mg G17-6.02 BID was determined to be maximum tolerated dose and the recommended dose for future studies.

The developed cream formulation of G17-6.07, named GZ21T to be used in this study, contains [REDACTED] of the drug compound (G17-6.07). **In Part A**, the start dose of [REDACTED]

[REDACTED] **In Part B**, the dose given in cohort 1 will be approximately 50% of the start dose in Part A and will not exceed the doses given in Part A in subsequent cohorts (optional cohorts 2 and 3).

The minipig skin is considered a most relevant model for human skin in terms of toxicity and absorption. In the 28-day dermal toxicity study in minipigs, the GZ21T [REDACTED] % cream was applied once or twice daily to skin areas corresponding to [REDACTED] % of BSA and in local concentrations of [REDACTED] mg (drug compound)/cm². The total doses administered per kg body weight (bw) were [REDACTED] mg/kg. No local tolerability issues or systemic effects were recorded in this study.

8.3.2 *Rationale for dose choices*

Refer to Section 8.3.1.

8.3.3 *Maximum dose*

The maximum dose used in the trial will not exceed █ GZ21T cream applied to █ BSA.

8.3.4 Stopping criteria for dose escalation (Part A)

Dose escalation and stopping criteria are shown in Table 8.3-1.

The Principal Investigator and the iSRC (see Section 8.3.5) will follow the recommendations and grading system of the common terminology criteria for adverse events (CTCAE) v5.0 [7] (see Section 11.3.1) as well as the recommendations published by *Sibille et al. (2010)* [8], which constitute an FIH adaptation of the grading systems previously proposed in the CTCAE v5.0, the World Health Organisation (WHO) recommendations for grading acute and subacute toxicity in cancer treatment [9], the National Institutes of Health (NIH) grading of severity of adult and paediatric AEs [10], and the US Food and Drug Administration (FDA) toxicity grading scale for healthy adult and adolescent volunteers included in preventive vaccine clinical trials [11]. The intensity grade and frequency of AEs will be considered (refer to Section 11.3.1).

Emerging trends or safety signals, which are not necessarily covered by the stopping criteria in Table 8.3-1 may warrant the scheduling of *ad hoc* iSRC meetings, after which the iSRC will make recommendations to the Sponsor on whether to stop dosing individual participants or certain cohorts, or whether to terminate the trial altogether.

No systemic toxicity was observed when GZ21T at doses up to [REDACTED] bw were applied topically to minipigs for 28 days. Furthermore, there was very low systemic exposure to GZ21T in the study. It is therefore difficult to establish stopping rules based on GZ21T exposure which have been reflected in the stopping rules defined in Table 8.3-1. A thorough evaluation with respect to safety criteria will be performed.

Table 8.3-1 Dose escalation and stopping criteria

No. Stopping criterion	Action taken
At the individual and cohort level	
1 If no participant has an serious adverse event (SAE) considered at least possibly related to the IMP administration, i.e. , a serious adverse reaction (SAR).	Escalate to the next higher dose level.
2 If 1 participant on active treatment has an SAE assessed as at least possibly related to IMP administration.	
1. Stop dosing the participant with a potential SAR. Await the dosing of additional participants until the iSRC's recommendation and the Sponsor's decision on continuation.
 
2. Unblind the participant with potential SAR. Only voting members of the iSRC will be unblinded.
 
3. Evaluation by the iSRC. The iSRC makes a recommendation to the Sponsor.
 
4. The Sponsor decides how to proceed.
 
The participant received active treatment, i.e., met the stop criterion: stop further dosing at this dose level for all participants. The Sponsor decides if the trial will be terminated or if dosing will resume at a lower dose level.

3 If 2 participants on active treatment in the same cohort have severe, non-serious AEs assessed at least possibly related to the IMP administration (independent of whether the AEs are within the same system organ class [SOC]).	
1. Stop dosing the participants with severe, non-serious potential ARs.
 
2. Unblind the participants with potential ARs. Only voting members of the iSRC will be unblinded.
 
3. Evaluation by the iSRC. The iSRC makes a recommendation to the Sponsor.
 
4. The Sponsor decides how to proceed.
 
Both participants received active treatment, i.e., met the stop criterion: stop further dosing at this dose level for all participants. The Sponsor decides if the trial will be terminated or if dosing should resume at a lower dose level.

Final dosing stop and termination of trial	
4 If 2 participants on active treatment have SAEs assessed as at least possibly related to IMP administration.	
1. Stop dosing the participants with potential SARs. Await dosing additional participants until the iSRC's recommendation and the Sponsor's decision on continuation.
 
2. Unblind the participants with potential SARs. Only voting members of the iSRC will be unblinded.
 
3. Evaluation by the iSRC. The iSRC makes a recommendation to the Sponsor.
 
4. The Sponsor decides how to proceed.
 
Both participants received active treatment, i.e., met the stop criterion: Termination of trial.
 
One (1) participant received active treatment, i.e., met stop criterion: See stop criterion no. 2.

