8.3.5 Internal Safety Review Committee (Part A)

The voting members of the iSRC will consist of the Principal Investigator, the CTC Medical Monitor and the Sponsor's Medical Representative. In addition, the trial clinical research manager, the trial pharmacokineticist and additional Sponsor representatives will be invited as appropriate and function as non-voting members. Other internal or external experts may be invited and consulted by the iSRC as appropriate.

Before initiating a new dose cohort, all participants in the previous cohort must have been treated and all available safety, tolerability, and plasma concentration data up until and including 24 hours after dosing must have been evaluated by the iSRC. After collection of the last available 24-hour data, there will be at least 1 week between dose escalations. In case of dropouts, available data for the dropouts will be included in the iSRC evaluation. If the GZ21T drug is considered safe and tolerable, the recommended next dose level, based on the predicted exposure, will be provided to the Sponsor in writing. Based on the emerging safety and plasma PK data, the amount of required data to be reviewed after each completed cohort may be adjusted. Likewise, the number of dose levels and planned sampling times may also be adjusted. These adjustments will be documented in non-substantial modifications to the CTP. Details regarding the timing of iSRC reviews and the data to be reviewed will be provided in a separate iSRC charter.

Sentinel dosing will be applied. The first 2 participants in each cohort will receive either GZ21T or placebo as randomised. After the sentinel participants, at least 24 hours must pass before dosing of the remaining participants to give sufficient time for the observation of any reactions.

An adaptive dosing strategy will be applied to allow for a flexible and safe dose escalation. The planned dose escalation is outlined in Section 8.3.2. The actual doses administered in each cohort will be guided by the iSRC recommendations based on the available safety, tolerability, and PK data, as described above. Every dose step is thus adjustable and the recommendation to the Sponsor may be to continue with a higher or lower dose than the planned dose, to repeat the same dose level, to continue with an intermediate dose level, or to stop dosing.

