11.3.2 Local tolerability

The Investigator will assess the incidence of local tolerability reactions of the administration site by direct inspection at visits and timepoints specified in Table 8.1-1 and Table 8.1-2 for Part A and in Table 8.1-3 for Part B. The assessment will include the Investigator's (or delegate's) evaluation of erythema, swelling, pruritus, burning and discoloration and dryness.

The presence/absence and intensity of local tolerability reactions at each time point will be recorded in a local tolerability module of the eCRF. Assessment of intensity will be performed as follows:

- Local tolerability reactions will be assessed by the Investigator or delegate as non, mild, moderate, or severe based on the definition of the reaction as outlined in Table 11.3-1. Discoloration is defined as change in skin tone other than erythema, *e.g.*, increased pigmentation or blanching, other than colour from the IMP. The intensity of each reaction will be documented in the eCRF.

Local tolerability reactions will be recorded as IMP-related AEs in the AE Log of the eCRF as follows:

- Erythema, swelling, pruritus, burning, blistering and urticaria: Grade 2 (moderate) and Grade 3 (severe) reactions **OR** Grade 1 if present \geq 24 hours after the start of IMP application.
- Dryness and discoloration: Grade 2 (moderate) and Grade 3 (severe) reactions.

As for other AEs, the full duration of the reaction(s), and the highest recorded intensity per reaction, should be entered.

Table 11.3-1 Local tolerability evaluation scale

Reaction	None=0	Mild=1	Moderate=2	Severe=3
Erythema	No detectable erythema; skin of normal colour	Slight pinkness present	Definite redness, easily recognised	Intense redness
Swelling	No swelling	Mild	Moderate	Severe
Pruritus	No pruritus	Occasional, slight itching/scratching	Constant or intermittent itching/scratching that is not disturbing sleep	Bothersome itching/scratching that is disturbing sleep
Burning	No burning	Slight warm, tingling sensation; not really bothersome	Definite warm, tingling sensation that is somewhat bothersome	Hot, tingling/stinging sensation that has caused definite discomfort
Blistering	None	Discrete signs	Moderate	Severe
Urticaria	None	Discrete signs	Moderate	Severe
Discoloration	None	Mild	Moderate	Severe
Dryness	None	Mild	Moderate	Severe

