5.2 Definition of analysis sets

The analysis sets defined for the trial are outlined in Table 4.

Table 4 Analysis sets

Analysis set	Definition	Comment	Use of analysis set
Full analysis set (FAS)	All enrolled participants who received IMP.	Participants will only receive 1 dose of IMP. Therefore, the phrase (as stated in the CTP) “at least 1 dose of” before “IMP” is removed from the definitions to minimise confusion.	Part A and Part B: Safety endpoints and description of trial population.
Pharmacokinetic analysis set (PKAS)	All randomised participants in Part A who received IMP and provided an evaluable plasma concentration profile, and who have no AEs or protocol deviations judged to affect the PK analysis. Individual PK values may be excluded from the analysis.		Part A: PK endpoints.

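### The stop row for two severe, related, non-serious AEs in a cohort does not hold dosing of the remaining participants while the decision is pending

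*Protocol*

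**What the plan says.** Table 8.3-1 in Protocol 8.3.4 has three stop rows, each with four numbered steps: immediate action, unblinding, iSRC evaluation, and the Sponsor's decision.

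- **Row 2** (one related SAE on active treatment): step 1 stops the affected participant and adds "Await the dosing of additional participants until the iSRC's recommendation and the Sponsor's decision on continuation".
- **Row 3** (two participants on active treatment in one cohort with severe, non-serious, related AEs): step 1 consists only of "Stop dosing the participants with severe, non-serious potential ARs".
- **Row 4** (two related SAEs on active treatment): step 1 stops the affected participants and adds "Await dosing additional participants until the iSRC's recommendation and the Sponsor's decision on continuation".

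Once active treatment is confirmed, rows 2 and 3 carry the same instruction: "stop further dosing at this dose level for all participants". Row 4 ends the trial.

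Two other provisions matter here. Protocol 8.3.5 sets a sentinel pause for the first two participants of each cohort: "at least 24 hours must pass before dosing of the remaining participants to give sufficient time for the observation of any reactions". SAP 5.2 notes that "Participants will only receive 1 dose of IMP".

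**The concern.** In a single-dose trial, a stop rule can protect only the people who have not yet been dosed. Row 3's immediate action concerns those who already have been. The criterion requires both participants to be on active treatment and Part A is blinded, so it cannot be confirmed before unblinding in step 2. Rows 2 and 4 cover that interval with a hold; row 3 leaves it open.

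Row 3 is also the row most likely to matter for a cream. On local tolerability findings, Protocol 11.3.2 states: "Local tolerability reactions will be recorded as IMP-related AEs in the AE Log of the eCRF as follows". Severe reactions are among those listed, and for intensity it adds: "As for other AEs, the full duration of the reaction(s), and the highest recorded intensity per reaction, should be entered". Unless such a reaction meets a seriousness criterion, two of them on active treatment in a cohort lead to row 3.

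At stake is the protection that sentinel dosing and the cohort stop rule are meant to give healthy volunteers who gain no medical benefit. As written, two severe related reactions do not by themselves pause the cohort.

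**Working it through.** **1. Row comparison.** Steps 2 to 4 are the same in substance in rows 2, 3 and 4. Step 1 differs: rows 2 and 4 stop the affected participants and hold the others, while row 3 only stops the affected participants. Row 3 shows no redaction mark or table break that would explain the difference.

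**2. Search for a hold elsewhere.**

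- The sentinel pause (8.3.5) is a fixed wait of at least 24 hours with no stated condition on what was observed.
- The iSRC review and the one-week gap (8.1, 8.3.5) apply before a new cohort, not within one.
- Ad hoc iSRC meetings (8.3.4) are optional.
- The temporary halt in 15.6 is at the Investigator's or Sponsor's discretion.
- The SAP contains no stopping rules.

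None of these is a mandatory hold within a cohort.

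**3. Timing.** Table 8.1-2 schedules local tolerability at 2, 8 and 24 hours after dosing. Severe reactions in both sentinels can therefore be known before the other six are dosed.

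**4. Who could still be dosed.** Each cohort has 8 participants allocated 6:2 (Protocol 9.3). If both sentinels trigger the row, 8 − 2 = 6 are undosed, of whom 6 − 2 = 4 are on GZ21T.

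**5. How often.** The plan gives no event rate and no dose spacing after the sentinels. Assume one block of 8 per cohort and an independent probability p of a severe related non-serious AE for each active participant.

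- Both sentinels active: C(6,2)/C(8,2) = 15/28 = 0.536.
- (a) Both sentinels active and both affected: 15/28 × p².
- (b) Upper bound, with dosing one at a time and every event seen before the next dose. Row 3 is met with at least one active participant undosed if two or more events fall among the first five of the six active participants: 1 − (1−p)⁵ − 5p(1−p)⁴.
- (c) If the four remaining active participants in the worst case were dosed, the chance of at least one further such event: 1 − (1−p)⁴.

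For p = 0.10: (a) 0.536 × 0.01 = 0.54%; (b) 1 − 0.5905 − 0.3281 = 8.15% (from unrounded terms); (c) 1 − 0.6561 = 34.4%.

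| Assumed p | (a) both sentinels | (b) upper bound | (c) further event among 4 |
|---|---|---|---|
| 1% | 0.005% | 0.10% | 3.9% |
| 5% | 0.13% | 2.3% | 18.5% |
| 10% | 0.54% | 8.15% | 34.4% |
| 20% | 2.14% | 26.27% | 59.0% |
| 30% | 4.82% | 47.18% | 76.0% |

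Column (b) is the chance that the gap opens, not that anyone is dosed in it, and usually fewer than four active participants would remain. Column (c) is conditional on the worst case having arisen and dosing having continued.

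**The case against.** **Silence is not an instruction.** No text says that dosing continues. The Investigator can halt, the Principal Investigator votes on the iSRC, and disagreement among voting members is resolved conservatively (8.3.5). A prudent site would probably pause. This stands as a limit on the practical effect, but none of it is mandatory, whereas rows 2 and 4 are.

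**A lighter interim response to non-serious events may be deliberate.** The documents do not settle whether this is a choice or a drafting slip. However, no rationale is given, and a confirmed row 3 stops the dose level for everyone, as row 2 does. A consequence of that weight justifies a short wait while allocation is checked.

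**The two severity scales are not reconciled.** AE intensity follows CTCAE v5.0 (11.3.1.10), where Grade 3 covers disabling events or those for which hospitalisation is indicated. Table 11.3-1 counts intense redness as severe. If CTCAE governs, some Grade 3 events would be serious and fall under row 2, which has a hold. If the local scale governs, milder reactions could trigger row 3. This stands as a caveat, although 11.3.2 itself labels severe local reactions Grade 3 and sends them to the AE log.

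**Rates of 10% to 30% may be too high.** Protocol 6.1.2 reports preliminary blinded data as generally well tolerated, and 8.3.1 reports no local tolerability issues in minipigs. This is a fair point, and the 1% and 5% rows of the table reflect it.

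**Conclusion.** The concern holds. Row 3 lacks the hold that rows 2 and 4 contain, its only immediate action has essentially no effect in a single-dose trial, and no other provision in the protocol or SAP requires a within-cohort pause. The exposure is limited to the interval between the second event and the Sponsor's decision, and arises only if participants are still undosed. The worst case of 6 undosed, 4 of them active, is probably uncommon: below 5% of cohorts even at an assumed 30% event rate, and far below 1% at 5% or less. The omission is certain from the text. The frequencies rest on assumed rates, independence, and one block per cohort. The separate iSRC charter was not available and might add a hold. The change should be made because it removes reliance on discretion at negligible cost.

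**What to change.** Add row 4's sentence to step 1 of row 3 in Table 8.3-1: "Await dosing additional participants until the iSRC's recommendation and the Sponsor's decision on continuation". With it, no further participant could be dosed while the decision is pending. The cost is one sentence in a protocol modification and, only if the row is triggered, a short pause in the cohort.
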